Study protocol

Infections in migrants: the importance of malaria and other parasites

2021-08-01

Study protocol

Infections in migrants: the importance of malaria and other parasites

Overall aim

The purpose of this project is to improve the health in migrants and immigrants focusing on malaria and other parasitic infections.

Specific aims

1. To assess the parasite prevalence in newly arrived migrants and the need to introduce screening for malaria and other parasites in migrants from certain countries.
2. To assess the parasite prevalence and specific antibody responses to malaria and other parasitic infections in immigrants who live in Sweden.

Background

Malaria is a major threat to human health, especially in Sub-Saharan Africa [1]. Global migration has resulted in a surge of refugees and asylum applications in Europe, many from malaria endemic countries.

The symptoms of malaria range from mild febrile illness to life-threatening multi-organ failure [3]. Disease severity is influenced by several host-parasite interactions, where host immunity is believed to be one of the most important [4].

Immunity to malaria is gradually acquired after repeated infections in populations living in high-endemic areas [4]. However, sterilizing immunity does not seem to evolve, and asymptomatic low-level infections are common. Individuals may carry a low grade parasitemia for extended periods of time [5]. Chronic parasitemia may lead to anaemia [6], cognitive dysfunction [7], adverse events during pregnancy [8] and may have hidden cost on telomere degradation and ageing [9].

Migrants from malaria endemic areas may present with febrile malaria but may also harbour asymptomatic malaria infection. Moreover, other parasitic infection can cause silent infections with adverse effect on health, such as schistosomiasis causing bladder calcification and strongyloides that may progress to a life-threatening disease called strongyloides hyperinfection, especially in patients receiving corticosteroids or other immunomodulatory treatment.

Thus, estimating the burden of malaria and other parasitic infections in newly arrived migrants as well as in immigrants with longer residency in Sweden is important in order to improve health in these populations.

Previous studies have reported 3-30% parasite prevalence in asymptomatic refugees from malaria endemic areas [11-14]. In Sweden, health screening is offered to newly arrived immigrants, including HIV, tuberculosis and viral hepatitis. Currently, malaria is not included in the screening program in

Sweden, although other countries recommend screening [15-17] and in the US, presumptive treatment is offered without testing [18]. Neither is there any regular testing for other parasites, not even preceding long term corticosteroid treatment.

Moreover, duration of asymptomatic parasite carriage in non-endemic countries is not fully established, however, case reports suggest that infections may persist for several years [20].

The immunologic response to malaria infection consists largely of antibodies towards a variety of parasite antigens, and develops over the course of several symptomatic malaria infections [22]. In highly endemic areas, immunity gradually protects against the severe forms of the disease and on further exposure, protection against clinical symptoms evolves [4, 22]. However, the protective immunity wanes over time with ceased exposure and thus previously protected individuals living in non-endemic countries are at risk for developing a more severe disease upon re-exposure for example when travelling to visit friends and relatives [23]. The longevity of circulating antibodies towards malaria is not fully elucidated, and therefore the risk cannot be fully appreciated.

This project focuses on the burden of malaria and other parasitic infections in newly arrived migrants and immigrants with longer residency in Sweden. We will evaluate the parasite prevalence and if screening for malaria and other parasites should be offered in migrants from Sub-Saharan Africa. In addition, we will assess longevity of malaria-specific immune responses as well as how migrants navigate through the Swedish health system.

Study design: Cross-sectional observational study.

Study population:

1. Newly arrived migrants born in countries where malaria is endemic (ie Sub-Saharan Africa) will be invited to participate in the study at migration health care units in Stockholm and Västerås. Blood samples will be collected at the time of routine sampling. According to sample size calculation based on expected 5% prevalence (see below) a total of 715 individuals will then be included in total. This number will be adjusted based on results in the pilot study.
2. Immigrants from malaria endemic countries living in Sweden will be invited to participate with voluntary blood sampling on one occasion. The study will be advertised in posters in waiting areas at health clinics in Stockholm.
3. Letter invitations to individuals arriving in Sweden from Democratic Republic of the Congo and Uganda between 2015 and 2019 and with a postal address in the Stockholm County, will be sent an invitation letter offering to participate in the study.

Inclusion criteria: Born in a malaria endemic country, defined as a country with indigenous spread of malaria reported in the World Malaria Report (WHO) 2019.

Exclusion criteria: Inability to understand patient study information or inability sign the informed consent form, with exception to children under 15 where legal guardian may approve and sign consent.

Sampling and analyses: A venous blood samples (EDTA tube) will be collected on one occasion. To minimize the amount of venipunctures and time for the study participants, blood samples will be collected on the same occasion as other blood samples taken within the routine screening program for newly arrived migrants. A short questionnaire including questions about patient origin and previous malaria as well as other diseases and previous treatment will be completed at the time of sampling with the aid of a translator if needed.

Blood samples will be sent to the research laboratory for malaria diagnostics and haemoglobin concentration. A rapid diagnostic test (RDT) will be performed for malaria. The sample will thereafter be centrifuged, aliquoted, and stored frozen at the research laboratory. Presence of parasites will be analysed by realtime-PCR of the species specific 18SRNA gene in a multiplex assay [25]. In study population 4, malaria microscopy will be performed at the same time as RDT to increase sensitivity.

RDT is less sensitive than microscopy and PCR but offers a rapid result, the same day with this set up, and all positive individuals will be referred to the Department of Infectious Diseases at the regional hospital for further investigations and treatment. Likewise, all individuals found to be positive for malaria by microscopy and/or PCR at a later stage will be contacted and referred for complete assessment and treatment at the Department of Infectious Diseases. Results from complete blood count will be assessed and followed up according to clinical routine at each centre where samples were collected.

Contact information to the study participant will be included as part of the recruitment and consent procedures in order to be able to contact the study participants for referral.

Complementary to the proposed study, health economic aspects of malaria screening will be assessed for cost-effectiveness estimation.

Moreover, PBMC will be prepared from a subset of patients to assess the cellular immune response. Plasma samples will be analyzed for the presence and levels of antibodies against crude whole *P. falciparum* parasite extract using ELISA, and against a panel of specific pre-hepatic and blood stage antigens using a multiplex Luminex [26]. The magnitude and breadth of antibody responses will be related to duration of residency in a malaria free country. This will allow us to estimate the long-term decay kinetics using a sero-epidemiological mathematical model [27]. In addition, serological markers for schistosomiasis and strongyloides will be analysed at the Public Health Agency of Sweden.

A subset of volunteers among immigrants living in Sweden (n=100) will be asked to contribute with a second blood sample after 6-12 months. This will allow us to estimate the long-term decay kinetics using a sero-epidemiological mathematical model [27].

Statistical analysis

The analyses will be performed using Stata version 14.2 (StataCorp, College Station, TX, USA). Categorical variables will be summarized by proportions, and the numerical variables by medians and interquartile ranges (IQR). In comparative analyses, categorical variables will be analyzed using the Pearson's chi-squared test, or the Fisher's exact test when appropriate. The Mann-Whitney's U-test will be used for comparing the distribution of numeric variables between two groups and the Kruskal-Wallis's test among multiple groups. Backward stepwise univariable logistic regression will be used to potential risk factors for parasitic infection. The variables with a p-value less than 0.05 will be

kept in the final multivariable model. The Wald's test will be used to test the regression coefficients. P-values less than 0.05 were considered statistically significant.

Significance

Migration health and integration is of great concern and importance. The level of asymptomatic parasite carriage is unknown in migrants arriving to Sweden, however, chronic asymptomatic malaria may later on result in symptomatic disease or cause another burden on the host. Thus, the findings in this project have the potential to guide the prevention and management of malaria in migrants.

Establishing the longevity and breadth of immune responses to malaria will contribute to vaccine design and will also help identification of populations at risk in areas of declining transmission and optimisation of sero-epidemiological models.

Results from the questionnaire will be able to guide improved web-based information to immigrants about health care of febrile illness after tropical visits and in newly arrived migrants. The research and dissemination of results will improve the management of fever and malaria in high risk groups including children, adults and pregnant women originating from malaria endemic areas.

Ethical considerations

There are several ethical considerations in the proposed research project, related both to the study design and features of the study population. The study is performed on human volunteers after informed consent. However, migrants arriving in Sweden from malaria endemic countries come from diverse backgrounds and experiences of health care in their former home countries that could significantly differ from the organisation of the Swedish health care system. In this context, information about the project and how it is different from the offered health care (screening for other diseases) needs extra attention.

We believe that bridging the cultural and language barriers will be possible with the aid of translators that are present during the health check-ups in the clinic. We have previously experienced that malaria is a well-known disease among individuals originating in malaria endemic areas and that it is not associated with any significant stigma, which will facilitate bilateral understanding.

Furthermore, advantages of better malaria interventions justify blood sampling with only minor discomfort. The possible benefits of the study will favour future migrants from malaria endemic countries.

References

1. *World Malaria Report 2016*. 2016, WHO.
2. SCB. Available from: <http://www.scb.se/contentassets/ae2169ea762240feadca8779dc3662a0/be0101-utrikes-fodda-fland-invar-2016.xlsx>.

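### Does the missing sample size calculation, with a pilot adjustment that has no stated rule, undermine the target of 715 newly arrived migrants?

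*Combined protocol and SAP*

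**What the plan says.** Study population, item 1, covers newly arrived migrants at migration health care units in two cities. Its target reads: "According to sample size calculation based on expected 5% prevalence (see below) a total of 715 individuals will then be included in total". The next sentence adds: "This number will be adjusted based on results in the pilot study". That is the only mention of a pilot.

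The Statistical analysis section, where a calculation would be expected, covers software, summaries, tests and logistic regression, and says nothing on sample size. The text runs on without a blacked-out part there. The Background cites earlier prevalences of 3-30% in asymptomatic refugees, so 5% lies near the low end of the range.

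The screening question is worded in two ways. The Specific aims refer to "the need to introduce screening for malaria and other parasites in migrants from certain countries", and the Background asks "if screening for malaria and other parasites should be offered in migrants from Sub-Saharan Africa". Sampling and analyses provides for "A short questionnaire including questions about patient origin and previous malaria".

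**The concern.** A reader who follows the cross-reference finds nothing. The confidence level, the margin, and whether that margin is absolute (points) or relative (a share of the prevalence) are all unstated. This matters once the pilot is read, because the two kinds of margin move the sample size in opposite directions when prevalence departs from 5%. A pilot prevalence is also noisy, so the adjustment could shrink the study by chance even if 5% is right.

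At stake would be the precision of the prevalence estimate behind the screening question, and the number of infections available for the risk-factor regression. The two wordings of the screening question raise a smaller doubt: a single pooled prevalence would not answer a country-by-country question.

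**Working it through.** **Inputs.** From the protocol: expected prevalence 5% and total 715 (Study population, item 1). Not in the protocol, so assumed here: the target precision, the pilot size m (50 to 400) and the adjustment rule.

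**Step 1: can 715 be reproduced?** The usual formula for estimating one proportion is n = z² p(1−p)/d², with p(1−p) = 0.05 × 0.95 = 0.0475.

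- 95% confidence, d = 1.6 points: 1.960² × 0.0475/0.016² = 712.8, so 713.
- 99% confidence, d = 2.1 points: 2.576² × 0.0475/0.021² = 714.6, so 715.
- 90% confidence, d = 1.5 points, 20% loss: 1.645² × 0.0475/0.015² = 571.2, and 571.2/0.8 = 714.

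The figure is plausible, but its basis cannot be identified from the document. The steps below use 95% and 1.6 points for illustration only.

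**Step 2: what could the pilot do?** Holding absolute precision gives n = 1.960² p(1−p)/0.016². Holding relative precision (1.6/5 = 32% of p) gives n = 1.960² (1−p)/(p × 0.32²).

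| Pilot prevalence | Absolute rule | Relative rule |
|---|---|---|
| 2% | 295 | 1,839 |
| 3% | 437 | 1,213 |
| 5% | 713 | 713 |
| 10% | 1,351 | 338 |

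Not every fall in n is a loss. If prevalence really is 3%, then 437 people give 1.960 × √(0.03 × 0.97/437) = 1.6 points, which is the assumed target. Precision is lost only when the pilot misleads.

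**Step 3: how often would chance alone cut n by more than half?** Take true prevalence as 5%, so pilot positives are Binomial(m, 0.05). The absolute rule halves n when p(1−p) < 0.0475/2 = 0.02375, that is, below 2.43%. The relative rule halves it when (1−p)/p < 19/2 = 9.5, that is, above 1/10.5 = 9.52%.

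| Pilot size | Absolute rule: positives | Probability | Relative rule: positives | Probability |
|---|---|---|---|---|
| 50 | ≤1 | 27.9% | ≥5 | 10.4% |
| 100 | ≤2 | 11.8% | ≥10 | 2.8% |
| 150 | ≤3 | 5.5% | ≥15 | 0.8% |
| 200 | ≤4 | 2.6% | ≥20 | 0.3% |
| 300 | ≤7 | 1.6% | ≥29 | 0.06% |
| 400 | ≤9 | 0.4% | ≥39 | 0.007% |

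A pilot of 50 has a 0.95⁵⁰ = 7.7% chance of no positives. The absolute formula then gives zero and the relative one is undefined, so no analyst could apply either one mechanically.

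**Step 4: what would a chance cut cost?** At n = 295 and true 5%, the half-width is 1.960 × √(0.0475/295) = 2.5 points, against 1.960 × √(0.0475/715) = 1.6 points at 715. In exact 95% intervals, 15/295 gives 2.9% to 8.3% and 36/715 gives 3.6% to 6.9%.

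**Step 5: does the adjustment damage validity?** I enumerated all outcomes with pilot participants counted in the total, for pilots of 50, 100, 150 and 200, true prevalence of 3%, 5% and 10%, and both rules. The sample size was kept at 715 when the pilot had no positives. Bias in the final prevalence ran from −0.24 to +0.30 points, and exact 95% interval coverage from 95.2% to 97.9%.

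**Step 6: the two wordings.** Study population, item 1, itself equates malaria-endemic countries with Sub-Saharan Africa, so the second wording is a natural reading of the first. Origin is collected by questionnaire, and the Statistical analysis section already plans proportions and comparisons between groups. A breakdown by origin needs nothing new.

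**The case for a change.** The strongest case for a change is that the protocol's own range of 3-30% makes an adjustment likely, while its direction depends on a choice the document leaves open. After a 3% pilot the two readings differ by 1,213/437 = 2.8-fold, and after a 10% pilot by 1,351/338 = 4-fold the other way. A few sentences would settle the matter, and a rule that the pilot may raise but not lower 715 would prevent chance shrinkage.

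It stands that the cross-reference leads nowhere and the pilot has no stated rule. A reader would be better served by one line giving the basis of 715 and, once the pilot is read, its result and the final number. That is a matter of reporting.

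The rest is weaker. Nothing in the protocol points to a relative margin, and the large multiples need one. A floor of 715 would fix as a minimum a number whose basis is unknown. Under the absolute rule it would enrol 715 − 437 = 278 more people after a 3% pilot and 715 − 295 = 420 more after a 2% pilot, without meeting any stated target that would otherwise be missed. That is a preference between cost and precision, on which reasonable teams differ.

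Nor can the effect on the regression be sized from malaria prevalence in this group alone. The model is for parasitic infection in general: "Backward stepwise univariable logistic regression will be used to potential risk factors for parasitic infection". The other study populations may contribute, and so may other parasites, since "serological markers for schistosomiasis and strongyloides will be analysed at the Public Health Agency of Sweden".

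**Conclusion.** The concern is correct about what is missing but does not call for a change. The stated 715 is not shown to be wrong; it agrees with a common precision target to within two people (713), and with another exactly. A chance cut of more than half is a real possibility only if the pilot is small. Under the absolute rule at a true 5% it falls from 28% at a pilot of 50 to 2.6% at 200 and 0.4% at 400, and it is lower throughout under the relative rule. Where it happens, the half-width grows from about 1.6 to 2.5 points, and the estimate and its exact interval remain sound.

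The protocol sets no prevalence threshold for recommending screening, so no documented decision is shown to turn on that difference in this cross-sectional observational study. The investigators hold both the calculation and the pilot result and can report them with the final number.

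The probabilities rest on the pilot sizes and adjustment rules assumed here; the half-widths and validity figures also rest on the back-solved 1.6-point target at 95% confidence. The documents fix none of these.

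### Does measuring schistosomiasis and strongyloides only by serology leave the aim on other parasites unanswerable?

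*Combined protocol and SAP*

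**What the plan says.** The Specific aims section sets two aims. Aim 1 is "To assess the parasite prevalence in newly arrived migrants and the need to introduce screening for malaria and other parasites". Aim 2 is "To assess the parasite prevalence and specific antibody responses to malaria and other parasitic infections in immigrants who live in Sweden". The Background repeats the screening question: "We will evaluate the parasite prevalence and if screening for malaria and other parasites should be offered in migrants from Sub-Saharan Africa". It also explains the interest in helminths: "other parasitic infection can cause silent infections with adverse effect on health, such as schistosomiasis causing bladder calcification and strongyloides that may progress" to severe disease.

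Under Sampling and analyses, direct detection is described for malaria. "A rapid diagnostic test (RDT) will be performed for malaria", and in one study population "malaria microscopy will be performed at the same time as RDT to increase sensitivity". For the molecular test, "Presence of parasites will be analysed by realtime-PCR of the species specific 18SRNA gene in a multiplex assay"; the reference cited for it (reference 25) is an assay for telling Plasmodium species apart. For the two helminths the single statement is that "serological markers for schistosomiasis and strongyloides will be analysed at the Public Health Agency of Sweden". The marker, cut-off and accuracy are not given.

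The Statistical analysis section summarises categorical variables by proportions. It plans logistic regression for parasitic infection without defining a case.

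**The concern.** Serological positivity and current infection are different quantities. If the markers are antibodies, a positive result may reflect a present infection, a past one or a false positive, and an infected person may test negative. The plan recognises this distinction for malaria: parasites are sought by PCR, while antibodies are studied separately and their decay is modelled against time since leaving an endemic area. Aim 2 also lists prevalence and antibody responses as two things.

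The Background gives silent infection as the reason to care about schistosomiasis and strongyloides. A reader could therefore take a seropositive proportion as the prevalence of untreated infection, and a screening recommendation could then claim more than the data support. The undefined regression outcome adds a second worry, that malaria PCR positives and helminth seropositives might be merged into one event.

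**Working it through.** **1. What each test measures.**

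| Test in the plan | Target | Kind of evidence |
|---|---|---|
| Rapid test | malaria | direct |
| Microscopy (one study population) | malaria | direct |
| 18S multiplex PCR | Plasmodium, by the title of reference 25 | direct |
| ELISA and Luminex | *P. falciparum* extract; panel of pre-hepatic and blood-stage antigens | antibody |
| Serological markers | schistosomiasis, strongyloides | serological, type not stated |

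The factual premise holds: no direct test for helminths is named.

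**2. What the aims promise.** In Aim 1 the words about other parasites attach to screening, and the sentence does not say whose prevalence is meant. The Background uses the term for malaria: it reports 3-30% in asymptomatic refugees, citing references 11-14, whose titles all concern malaria or Plasmodium. On that reading, direct malaria testing supplies parasite prevalence and serology informs the screening question for other parasites. The broader reading, prevalence of every parasite, is also possible. The wording is ambiguous, so a contradiction is not established.

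**3. Who is tested.** Where the plan restricts a procedure it says so: cell preparation in a subset, a second sample in n=100, microscopy in one population. The serology sentence has no restriction, so the natural reading is all participants.

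**4. Whether the error is in the plan.** No sentence equates a positive serology with current infection, and none says that helminth and malaria positives will be pooled.

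**5. Size.** The plan gives no helminth figure to reproduce. Its one design figure, 715 at an expected 5%, is not tied to helminths. It corresponds to a 95% half-width of 1.96 × √(0.05 × 0.95 / 715) = 0.016, or 1.6 points, and has no bearing on this question. Everything below uses assumed inputs.

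Let s be seroprevalence, q the share of seropositives currently infected and r the share of seronegatives currently infected. Current infection = s·q + (1 − s)·r. With s = 0.10:

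- r = 0: q = 0.25, 0.50, 1.00 gives 2.5%, 5.0%, 10.0%.
- r = 0.02: add 0.90 × 0.02 = 1.8 points, giving 4.3%, 6.8%, 11.8%.

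In the other direction, take 5% current infection with sensitivity and specificity (for current infection) of 0.90. Seropositivity = 0.05 × 0.90 + 0.95 × 0.10 = 0.045 + 0.095 = 14.0%. The share of seropositives who are infected is 0.045 / 0.140 = 32%. Over infection of 2-10%, sensitivity 0.80-0.95 and specificity 0.85-0.99, that share runs from 10% to 91%.

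These ranges show that the two quantities can differ widely. They do not show how far they differ here, or in which direction.

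**6. What a repair would alter.** Naming the marker, labelling the result and attaching an interval use data already planned. For example, 72/715 positive gives 10.1% (95% score interval 8.1% to 12.5%), and 10/100 gives 10.0% (5.5% to 17.4%). Both counts are assumed. Neither the specimens nor the tests change.

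**The case for a change.** The strongest case for a change is that other parasites belong to a decision aim, the repair is a few lines of text, and the sponsor already separates parasites from antibodies for malaria. That is a fair description of the text. It also stands that current helminth infection is not directly measured if the markers are antibodies, and that the regression outcome has no case definition.

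What does not stand is the step from there to a faulty plan. The Background identifies the lack of regular testing for other parasites, including before prolonged steroid therapy, as the gap. For the question whether to offer a blood test, the proportion positive on such a test is relevant evidence, though incomplete. The feared harm depends on someone later misreading an unlabelled proportion. Separate models for each infection would forbid a pooling that the plan never states.

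One tempting repair would do damage. Reserving the term parasite prevalence for malaria PCR would leave out people positive by rapid test or microscopy, whose results the plan acts on, and no reason for leaving them out appears in the documents.

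**Conclusion.** No change to the plan is needed. The description of the helminth measurement is thin and the aims are loosely worded, but the design does not contradict itself and no stated analysis is wrong. Analysts can be expected to name the test, report schistosomiasis and strongyloides results as seroprevalence with confidence intervals unless the marker detects current infection, model each infection separately, and say that the screening conclusion for these parasites does not by itself establish current infection.

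The size of the issue cannot be derived from the documents; the figures above are illustrations on assumed inputs. Malaria results are unaffected. The conclusion assumes that seropositivity will not be presented as current infection and will not be merged with malaria positives in one outcome. A statement in the plan to do either would change it.

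### If haemoglobin is compared by parasite status, the plan's general rule gives an unadjusted rank test across children, women and men, which mixes age and sex with any parasite effect

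*Combined protocol and SAP*

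**What the plan says.** All references are to the combined protocol and SAP.

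- **Background:** "Chronic parasitemia may lead to anaemia". Cognitive dysfunction, pregnancy complications and telomere damage are also listed. Of these four, only anaemia has a related measurement in the plan.
- **Sampling and analyses:** "Blood samples will be sent to the research laboratory for malaria diagnostics and haemoglobin concentration". No subset is specified. A complete blood count is mentioned separately, for clinical use only: "Results from complete blood count will be assessed and followed up according to clinical routine at each centre".
- **Exclusion criteria:** inability to consent excludes, "with exception to children under 15 where legal guardian may approve and sign consent". No age limit is given, and neither sex nor pregnancy is an exclusion.
- **Statistical analysis:** numeric variables are summarised by median and IQR. For two groups, "The Mann-Whitney's U-test will be used for comparing the distribution of numeric variables between two groups"; for more than two, Kruskal-Wallis. The one regression is for infection as outcome: "Backward stepwise univariable logistic regression will be used to potential risk factors for parasitic infection". The significance level is stated as "P-values less than 0.05 were considered statistically significant", without sidedness.
- **Study design:** cross-sectional and observational, so nothing balances infected and uninfected participants on age or sex.

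The section has no haemoglobin model, no stratified test and no anaemia definition. The questionnaire topics listed under Sampling and analyses are origin, earlier malaria, other diseases and earlier treatment. Age, sex and pregnancy are not named.

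**The concern.** Haemoglobin is measured alongside the malaria tests, and anaemia is the first harm that the Background lists. The obvious use of the data is to ask whether carriers have lower haemoglobin than non-carriers. Under the general rule, that question would be put to a test with no covariates.

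Haemoglobin differs between children, women and men, and changes in pregnancy. If carriers have a different age and sex mix from non-carriers, the raw comparison picks up that mix. More children among carriers would look like a parasite effect; more men among carriers would offset a real one. The logistic model does not help, because haemoglobin is not its outcome.

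At stake is the reading of a secondary result on the burden of silent infection. The parasite prevalence in the aims does not depend on it.

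**Working it through.** **The plan's own figure.** There is none for haemoglobin. The 715 newly arrived migrants cannot be reproduced from stated inputs, because only the expected 5% prevalence is given. An assumed 95% interval of ±1.6 points gives 1.96² × 0.05 × 0.95 / 0.016² = 713, but that half-width is back-solved. Here 715 serves only as the sample size.

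**Inputs from the documents.** n = 715; prevalence 5%, so 0.05 × 715 ≈ 36 infected and 679 uninfected; level 0.05 (two-sided assumed). The reported range of 3–30% gives about 21 to 214 infected.

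**Assumed inputs (none in the documents).** Uninfected mix of children/women/men 25/35/40%; mean haemoglobin 120/130/150 g/L (wide gaps) or 124/130/143 g/L (narrow gaps); within-group SD 12 g/L; a range of infected mixes.

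**Step 1: difference due to mix alone, wide gaps.**
- Uninfected mean: 0.25 × 120 + 0.35 × 130 + 0.40 × 150 = 135.5.
- Infected mix 40/32/28: 48.0 + 41.6 + 42.0 = 131.6, a difference of −3.9 g/L with no parasite effect.
- Infected mix 15/25/60: 18.0 + 32.5 + 90.0 = 140.5, a difference of +5.0 g/L.

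**Step 2: standard errors.**
- Between-group variance: 0.25 × 15.5² + 0.35 × 5.5² + 0.40 × 14.5² = 154.75.
- Unadjusted SD: √(144 + 154.75) = 17.3. SE: 17.3 × √(1/36 + 1/679) = 17.3 × 0.171 = 2.96 g/L.
- Adjusted SE: about 12 × 0.171 = 2.05 g/L.

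By normal approximation, −3.9/2.96 = −1.32 gives about 26% rejection with no true effect. A true 8 g/L deficit with equal mixes gives 8/2.96 = 2.70, about 77% power, against 8/2.05 = 3.90, about 97%, after adjustment.

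**Step 3: simulation of the Mann-Whitney test** (2,000 studies per setting, 36 infected against 679 uninfected). Entries are the percentage of studies with p < 0.05.

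| Infected mix (child/woman/man, %) | No effect, wide gaps | No effect, narrow gaps | 8 g/L deficit, wide gaps | 8 g/L deficit, narrow gaps |
|---|---|---|---|---|
| 25/35/40 (same) | 5.6 | 4.6 | 73 | 87 |
| 33/35/32 | 14 | 10 | 92 | 96 |
| 40/32/28 | 27 | 17 | 97 | 99 |
| 50/27/23 | 53 | 33 | 99 | 99.8 |
| 15/25/60 | 41 | 25 | 12 | 44 |
| 10/20/70 | 75 | 50 | 4 | 21 |

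In the last two rows the no-effect rejections arise because carriers appear to have higher haemoglobin. A linear model adjusted for the three groups rejects in about 4–6% of studies with no effect and detects the deficit in about 97%, whatever the mix. The data were generated from that model, so this is its best case.

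**Step 4: prevalence range, wide gaps.** Over the unbalanced mixes, rejection with no effect runs from 10% to 52% with 21 infected and from 41% to 100% with 214. A larger infected group makes the problem worse.

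**Step 5: the same point as infection ratios.** Take means of 120/130/148 g/L and 5% prevalence. If children are infected twice as often as adults, the infected mix is 0.50/0.35/0.40 divided by 1.25, or 40/28/32%, with mean 131.8 against 134.7 overall. The difference from the uninfected is (131.8 − 134.7)/0.95 = −3.1 g/L. In 3,000 simulated studies the test rejected in 20%. Three times as often gives −5.2 g/L and 44%. With equal risk in all groups it rejected in 4.8%.

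**The case against.** The strongest reply is that the criticised comparison is inferred. The protocol nowhere says that haemoglobin will be compared by parasite status; the rule covers numeric variables in general and names none. Haemoglobin is in neither specific aim. This stands, so the point is conditional: if the comparison is made, the written rule makes it unadjusted.

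A second reply is that the Mann-Whitney test does what it claims. If carriers are younger, the two haemoglobin distributions really do differ, and rejecting is correct. This also stands. The test is not invalid; the fault would lie in reading its result as an effect of the parasite. A reader might infer that the plan could declare anaemia where there is none. The documents do not support that: the test classifies nobody as anaemic, and no cut-off is stated that could be wrong.

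Third, every haemoglobin level, mix and infection ratio above is assumed. The documents do not say how many children will enrol or whether carriage varies with age or sex, and with equal mixes the test keeps its 5% level. This limits what can be said about size. It does not remove the loss of power, which needs no imbalance.

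Fourth, the methods paragraph is brief about every secondary variable. True, but haemoglobin is singled out for measurement, and here the stated default has an identifiable weakness with a simple remedy.

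**Conclusion.** The point holds in conditional form and is a cheap improvement. As written, the plan offers only an unadjusted rank test for haemoglobin by parasite status in a mixed-age, mixed-sex observational sample. With about 36 positives among 715, moderate imbalance raises rejection with no true effect from 5% to roughly 10–50%; the most extreme mix tried, with wide gaps, reaches 75%. An excess of men among carriers can cut detection of an 8 g/L deficit from 73% to 4–12% (wide gaps) or from 87% to 21–44% (narrow gaps). With no imbalance, the cost is power: 73% or 87%, against about 97% adjusted. These sizes rest on assumed haemoglobin levels and mixes. The documents establish only that confounding is possible and not dealt with.

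A reader might go further and infer that the case for screening rests on this comparison. The documents do not support that. Aim 1 ties screening to parasite prevalence, a cost-effectiveness assessment is described as complementary, and harm is drawn from cited literature. The prevalence estimate is unaffected.

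**What to change.** Add to Statistical analysis, for example: *If haemoglobin is compared by parasite status, linear regression adjusted for age group and sex, and for pregnancy where recorded, will be used (or a van Elteren test stratified by age-sex group). Any classification of anaemia will use age- and sex-specific cut-offs, fixed in advance. Unadjusted medians and IQRs will be shown by age-sex group as description.* If no such comparison is intended, say so and state what haemoglobin is for.

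The text costs one short paragraph. Two practical limits apply. Age, sex and pregnancy are not among the named questionnaire topics, so the sponsor should confirm that age and sex are recorded and add one pregnancy item if needed; pregnancy may not be recoverable later. With about 36 positives, spread as 9/13/14 over children, women and men at the assumed 25/35/40% mix, age groups must be broad and covariates few. Adjustment for age and sex will not remove other differences between carriers and non-carriers, so the result should still be reported as an association.
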